6.1.8 Exposure and Compliance to Study Treatment

Dose exposure and the compliance for treatment groups A1, A2 and A3 will be analyzed for SAF, modified SAF and FAS. The treatment duration, extent of exposure and compliance will be summarized by treatment group.

6.1.8.1 Treatment duration

Treatment duration is calculated from eCRF page ‘Study Drug Exposure.’ Missing dates are not replaced, i.e. subjects with missing date of first or last tablet of TP will result in missing treatment duration of respective TP.

Treatment duration per TP (TP_x, x=1,..., n) excluding breaks is defined as the number of days from the day of first drug administration until the day of last drug administration during the respective TPs, i.e. Date of last tablet of TP_x – Date of first tablet of TP_x +1. For treatment group A2, treatment duration excluding breaks by TP will be calculated based on a 168-day period. Overall treatment duration excluding breaks is the sum of available treatment durations of all TPs.

Overall treatment duration including breaks is defined as reference end date – reference start date + 1 without missing data replacement.

Treatment duration for subjects in treatment group B is defined as reference end date – reference start date + 1 without missing data replacement.

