4.5 Data Rules

Reference Start/End dates

For vilaprisan (VPR), the reference start and end dates refer to the first and last study drug intake and will be identified based on the eCRF entry (EXCATN=1). For subjects with study drug exposure unknown, the randomization date will be used as the reference start date, and the end date of last scheduled/ unscheduled visit according SV (Subject Visits dataset) will be used as the reference end date.

Missing or partially missing eCRF end dates will be replaced by the date of the last study drug intake according to the diary. In case there is no study drug intake recorded in the diary, the date of the last available visit/contact will be used, which is the maximum of the end date of last scheduled/ unscheduled visit according SV (Subject Visits dataset), and the “last visit” as collected on the eCRF page for Disposition dataset. For subjects randomized to VPR who did not take any treatment (FAS not SAF), the last available visit date will be used as the reference start date and the reference end date.

For treatment group B the reference start date is defined by the randomization date. The reference end date is defined by the start date of the End of Treatment (EoT) visit (unscheduled EoT visits not considered). Missing EoT visit dates will be replaced by the end date of the last available visit before the safety closeout visit (refer to Table 4-1). If a subject in treatment group B has no safety

closeout visit, missing EoT visit dates will be replaced by the date of last scheduled/ unscheduled visit according SV (Subject Visits dataset).

For both VPR and treatment group B, the reference end date after the missing replacement with the rules defined above should be no earlier than the reference start date. Otherwise, the reference end date will finally be replaced by the reference start date.

For any analysis, if date of first study drug exposure/ date of last study drug exposure is used, the reference start/end date for treatment group B defined as above will be used for the analysis in treatment group B, if applicable.

Table 4-1 Replacement rules for missing reference start/end dates and TP start/end dates

	Choice	VPR regimens	Treatment group B
Reference start date	1 st	eCRF	Randomization date
	2 nd	a. If study drug exposure unknown, use randomization date b. If no study drug exposure (FAS not SAF) use SV last visit end date	
Reference end date / Last TP end date	1 st	eCRF	EoT visit start date

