6.5.2.2 Endometrial thickness

For endometrial thickness the following time intervals will be considered:

- Intervals A (according to [Figure 4-1](#))
- Intervals C (according to [Figure 4-1](#))
- Exit examination

Number of subjects with ultrasound performed will be presented.

Summary statistics for change from baseline in endometrial thickness will be provided. In addition, the proportion of subjects with endometrial thickness > 18 mm will be investigated. A subgroup analysis by exposure group (treatment duration <=90 days, 91 to 180 days, etc.) will present the proportion of subjects with endometrial thickness > 18 mm and cyst like structure either ovary >= 3cm.

To investigate the correlation of endometrial thickness and biopsy results, the proportion of biopsies with hyperplasia without atypia (WHO 2014), atypical hyperplasia / EIN (WHO 2014), PAEC

present, PAEC not present, Extensive cysts present, and Extensive cysts not present will be presented for endometrial thickness > 18mm in ultrasound and endometrial thickness ≤18 mm in ultrasound.

6.5.2.3 Percentage change from baseline in BMD measured, hip, and femoral neck by DEXA

The percentage change in BMD of hip, and femoral neck will be summarized in the same way as described for the primary safety variable.

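### Overall treatment duration excluding breaks counts an undated vilaprisan course as 0 days, which shortens exposure and pushes overall compliance above 100%

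*SAP*

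**What the plan says.** Section 6.1.8.1 of the SAP takes treatment duration from the exposure page of the eCRF and does not replace missing dates: "subjects with missing date of first or last tablet of TP will result in missing treatment duration of respective TP". The total over courses is nevertheless formed: "Overall treatment duration excluding breaks is the sum of available treatment durations of all TPs".

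Two further durations are defined there. Vilaprisan duration including breaks runs from reference start to reference end. The group B rule begins "Treatment duration for subjects in treatment group B is defined as reference end date", and both formulas end "reference start date + 1 without missing data replacement".

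Section 4.5 does replace these dates for other purposes. For the end of vilaprisan treatment: "Missing or partially missing eCRF end dates will be replaced by the date of the last study drug intake according to the diary". For earlier TPs it also takes the last diary intake within the TP. For group B, "The reference end date is defined by the start date of the End of Treatment (EoT) visit (unscheduled EoT visits not considered"; the fallback is: "Missing EoT visit dates will be replaced by the end date of the last available visit before the safety closeout visit".

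Section 6.1.8.2 sums diary tablets over all TPs, with missing entries set to 0. It sums eCRF tablets over the TPs that have a count. Section 6.1.8.3 divides each sum by the overall duration excluding breaks.

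Section 6.5.2.2 plans "A subgroup analysis by exposure group (treatment duration <=90 days, 91 to 180 days, etc", without saying which of the durations is meant.

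**The concern.** Leaving a date unreplaced is a defensible choice. Summing what is left is not the same choice: in the total it assigns 0 days to a course that was taken. The result is then shown as an observed value, so the number of subjects in the overall row does not reveal it. If the last date is the missing one, the same woman has no duration including breaks but a duration excluding breaks that is too short.

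The shortfall is one whole course, so it differs by regimen and is largest in A2, where a course is 168 days. It carries into overall compliance, whose numerator and denominator may cover different courses. It may also carry into the display of endometrial thickness above 18 mm by exposure group.

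**Working it through.** The SAP states no duration or compliance figure to reproduce, so its rules are applied to a constructed subject.

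**Inputs.** From the design overview in section 3, one-year schedule: A1 has 4 courses of 84 days, A2 has 2 of 168 and A3 has 3 of 84. For A2, section 6.1.8.1 keeps the 168-day course as the unit. Assumed: one tablet taken and entered in the diary on every planned day, and exactly one course with a missing first or last tablet date.

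**Formulas.** With n courses of L days:
- actual days = nL; SAP total = (n − 1)L
- shortfall = 1/n
- overall diary compliance = nL / ((n − 1)L) = n/(n − 1)

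| Group | Actual days | SAP total | Shortfall | Diary compliance |
|---|---|---|---|---|
| A1 | 4 × 84 = 336 | 3 × 84 = 252 | 25% | 336/252 = 133% |
| A2 | 2 × 168 = 336 | 1 × 168 = 168 | 50% | 336/168 = 200% |
| A3 | 3 × 84 = 252 | 2 × 84 = 168 | 33% | 252/168 = 150% |

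Because treatment was stopped early, many women will have fewer courses, and one undated course then weighs more. With two courses in A1 or A3, the total is 84 instead of 168 days and compliance is 200%. With a single undated course nothing remains to sum, and the SAP does not say whether the overall value is 0 or missing.

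**eCRF compliance.** It is inflated in the same way if the undated course has a tablet count. In the reverse case, with dates complete and one course's count missing, it is (n − 1)/n: 75% in A1, 50% in A2 and 67% in A3.

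**Exposure group in 6.5.2.2.** Two 84-day courses give 168 days (the 91 to 180 group). With one undated the total is 84 days (the lowest group). This applies only if duration excluding breaks defines the groups.

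**Group means.** The SAP gives no frequency of missing dates. If a fraction f of subjects who completed the one-year schedule has one undated course, the mean is understated by f/n:

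| f (assumed) | A1 | A2 | A3 |
|---|---|---|---|
| 2% | 0.5% | 1.0% | 0.7% |
| 5% | 1.25% | 2.5% | 1.7% |
| 10% | 2.5% | 5.0% | 3.3% |

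**The case against.** The strongest defence is that 6.1.8.1 is a deliberate, written exception to 4.5. Recorded exposure dates are a legitimate basis for an exposure table, data are cleaned before analysis, durations are listed by subject, and missing tablet dates may be rare. All of that stands, and it limits the size of the problem. It does not justify the summing rule, which reports a partial total as a complete one.

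A reader might infer more than the SAP supports:

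- *That every other analysis uses replaced dates.* Compliance in 6.1.8.3 uses the same unreplaced durations.
- *That undated courses are recorded as zero.* The duration by TP is missing; the zero effect arises only in the overall sum.
- *That the rules lengthen group B while shortening vilaprisan.* Group B has no breaks, so its counterpart is vilaprisan duration including breaks. The two formulas are identical, and both lose a subject whose end date is missing.
- *That group B exposure is overstated.* A woman without a scheduled EoT date does drop out of the duration summary, though she stays in the FAS and SAF. How many such women there are, and whether they stopped early, is not in the SAP.
- *That Table 4-1 should simply be applied throughout.* Its third choice for vilaprisan is the last visit, with the safety closeout visit not excluded, so months off drug could count as treatment. Exposure is also summarised on the FAS, where never-treated women have both reference dates set to the last visit; the formula would give them a duration of 1 day.

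**Conclusion.** The point holds for the overall total excluding breaks and for what is built on it. For a fully adherent one-year subject with one undated course, the total is 25% (A1), 50% (A2) or 33% (A3) too short, and overall diary compliance is 133%, 200% or 150%. These figures follow from the rules and the planned schedule, given complete diary entries. The effect on group means depends on an unknown frequency: 0.5% to 5% if 2% to 10% of subjects are affected.

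This is a minor point. It is confined to descriptive exposure and compliance tables and, depending on which duration is meant, the exposure grouping in 6.5.2.2. AE classification and the primary BMD windows have their own date rules and are not affected. For group B, neither size nor direction of any effect can be determined from the SAP.

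**What to change.** 1. In 6.1.8.1, where a TP's last-tablet date is missing, use the last diary intake in that TP, as 4.5 already does, and report how many dates were replaced.
2. If a started TP still has no duration, for instance because its first-tablet date is missing, set overall duration excluding breaks and overall compliance to missing.
3. In 6.1.8.3, restrict numerator and denominator of overall compliance to the same TPs.
4. In 6.5.2.2, state which duration defines the exposure groups.
5. Do not use the last-visit fallback for vilaprisan, or the reference dates of never-treated women, as treatment duration.
6. For group B, show duration with the 4.5 end date (last visit before the safety closeout) next to the unreplaced version, with the number of subjects lacking an EoT date.

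The cost is SAP wording and small programming changes, since the diary-based dates and the group B end dates are already derived. The downside is that a few durations will rest on diary dates and a few totals will become missing; the reported counts make both visible.

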6.1.8.2 Extent of exposure

Extent of exposure of each TP is defined as the number of tablets taken during the respective TPs, using information from the Study Drug Accountability eCRF page and eDiary-entry respectively.

Missing number of tablets taken based on the eCRF page will not be replaced, i.e. subjects with any missing number of tablets taken for a pack dispensed based on the eCRF page will result in missing extent of exposure of respective TP. For treatment group A2, extent of exposure by TP will be calculated based on 168-day period. Overall extent of exposure based on the eCRF is the sum of available extent of exposure of all TPs.

Missing number of tablets taken based on eDiary-entry will be replaced with 0. Overall extent of exposure based on eDiary is the sum of the extent of exposure of all treatment periods.

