B	SCR up to 90 days	RND	Symptomatic nonhormonal medical treatment as determined by the investigators and/or watch and wait														12 wk FUP	

Groups A1, A2, and A3 treated daily with vilaprisan 2 mg during treatment periods
 Group A1: 4/8 treatment periods of 12 weeks, each separated by 1 bleeding episode (3/1 regimen)
 Group A2: 2/4 treatment periods of 24 weeks, separated by 2 bleeding episodes (6/2 regimen)
 Group A3: 3/6 treatment periods of 12 weeks, each separated by 2 bleeding episodes (3/2 regimen)
 Group B treated with standard of care (SoC) symptomatic nonhormonal medical treatment as determined by the investigators and/or watch and wait.
 B = bleeding episode; FUP = follow-up; RND = randomization; SCR = screening; trt = treatment; wk = week.

The **primary safety variable** is the percentage change in bone mineral density (BMD) of lumbar spine from baseline to about one year after start of treatment (SoT) (please refer to section 6.5.1 for details). With the implementation of Protocol Amendment 10 (version 7.0), the study is being prepared for closure. A thorough safety monitoring is performed in subjects before this closure, including a recovery BMD scan. All subjects who received vilaprisan treatment will be asked to undergo a BMD scan at least 6 months after the last intake of vilaprisan, to document absence of

bone loss or adequate recovery after the end of treatment. Subjects randomized to treatment group B who are still in the study with implementation of Protocol Amendment 10 (version 7.0) should also undergo a BMD scan at the safety closeout visit, unless they had a BMD scan performed within the last 3 months prior to the safety closeout visit.

4. General Statistical Considerations

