6.1.8.3 Treatment compliance

Treatment compliance of study drug is calculated on the basis of both eCRF (i.e. data collected from drug accountability and study drug exposure pages) and eDiary-entry respectively.

Treatment compliance based on the eCRF by TP is defined as

$$\left(\frac{\text{Extent of exposure in TPx (eCRF)}}{\text{Treatment duration in TPx excluding break(eCRF)}} \right) \times 100\%, \text{ where } x=1, \dots, n.$$

Overall treatment compliance based on eCRF is calculated as

$$\left(\frac{\text{Overall extent of exposure(eCRF)}}{\text{Overall treatment duration excluding breaks(eCRF)}} \right) \times 100\%.$$

Treatment compliance based on eDiary-entry by TP is defined as

$$\left(\frac{\text{Extent of exposure in TPx (eDiary)}}{\text{Treatment duration in TPx excluding break(eCRF)}} \right) \times 100\%, \text{ where } x=1, \dots, n.$$

Overall treatment compliance based on eDiary is calculated as

$$\left(\frac{\text{Overall extent of exposure(eDiary)}}{\text{Overall treatment duration excluding breaks(eCRF)}} \right) \times 100\%.$$

For treatment group A2, treatment compliance by TP will be calculated based on a 168-day period.

Data on duration of treatment, compliance, and used tablets will be presented by listings.

Extent of exposure and treatment compliance for treatment group B will not be analyzed.

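### Overall eCRF compliance (SAP 6.1.8.3) can divide tablets from one set of treatment periods by days from another, so a missing pack count acts as zero tablets and a missing date inflates the ratio

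*SAP*

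**What the plan says.** Three subsections of the SAP combine to define overall eCRF compliance for groups A1, A2 and A3.

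- **Duration (6.1.8.1).** "Treatment duration is calculated from eCRF page" 'Study Drug Exposure'. Missing dates are not replaced: "subjects with missing date of first or last tablet of TP will result in missing treatment duration of respective TP". Then: "Overall treatment duration excluding breaks is the sum of available treatment durations of all TPs".
- **Tablets (6.1.8.2).** Extent of exposure is the number of tablets taken, "using information from the Study Drug Accountability eCRF page and eDiary-entry respectively". On the eCRF side missing counts are not replaced: "subjects with any missing number of tablets taken for a pack dispensed based on the eCRF page will result in missing extent of exposure" for that TP. Then: "Overall extent of exposure based on the eCRF is the sum of available extent of exposure of all TPs". On the eDiary side, by contrast, a missing number is set to 0.
- **Ratio (6.1.8.3).** "Overall treatment compliance based on eCRF is calculated as" overall eCRF extent of exposure over overall eCRF duration excluding breaks, times 100%. The overall eDiary ratio uses the same denominator.

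For A2, exposure, duration and compliance by TP are all built on the 168-day protocol TP. Section 6.1.8 summarizes these variables by treatment group on the SAF, modified SAF and FAS.

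**The concern.** The two sums have different rules for leaving a TP out, and their inputs come from two different eCRF pages, so one can be missing without the other. No sentence ties the sums to a common set of TPs, and none sets the overall ratio to missing when they differ.

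When a TP has dates but an incomplete pack count, its days stay in the denominator while its tablets vanish from the numerator. That is arithmetically the same as imputing 0 tablets, although 6.1.8.2 says missing eCRF counts are left unreplaced and reserves replacement by 0 for the eDiary. When a TP has a count but lacks a date, its tablets stay and its days vanish, so the ratio is too high.

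At stake is whether the overall eCRF compliance tables describe adherence or gaps in data capture. A subject could show 100% in every evaluable TP and far less, or far more, overall.

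**Working it through.** The SAP states no compliance figure, so there is none to reproduce. The check applies its formulas to a subject who takes one tablet on every treatment day, so true compliance is 100%.

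**Inputs** (SAP Section 3, notes to Figure 3-1, one-year plan; 12 weeks = 84 days, 24 weeks = 168 days)

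- A1: 4 TPs of 84 days, 336 days in total
- A2: 2 TPs of 168 days, 336 days in total
- A3: 3 TPs of 84 days, 252 days in total

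**Formula as written**

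Overall eCRF compliance = 100 × (sum of tablets over TPs with complete counts) / (sum of days over TPs with both dates).

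For *k* TPs of equal length and full adherence:

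- *m* TPs lack a count and all dates are known: 100 × (*k* − *m*)/*k*
- *d* TPs lack a date and all counts are known: 100 × *k*/(*k* − *d*)

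**Results with one TP affected**

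| Group | One TP count missing | One TP date missing |
|---|---|---|
| A1 | 252/336 = 75.0% | 336/252 = 133.3% |
| A3 | 168/252 = 66.7% | 252/168 = 150.0% |
| A2 | 168/336 = 50.0% | 336/168 = 200.0% |

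With more than one count missing, A1 falls to 50.0% (two) or 25.0% (three), and A3 to 33.3% (two).

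**Effect of the early stop.** An A1 or A3 subject with three 84-day TPs and one missing count shows 168/252 = 66.7%; with two TPs, 84/168 = 50.0%. The fewer TPs a subject started, the more each missing count weighs.

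**Case where no error arises.** If the same TP lacks both its count and a date, it leaves both sums. In A1 that gives 252/252 = 100%.

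**By-TP ratio.** A missing count or a missing duration makes that TP's eCRF ratio missing, so no false value is produced.

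**eDiary ratio.** Its numerator does not depend on pack counts, so the first column does not apply. Its denominator is the same eCRF duration, so the second column does.

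**With matched TPs.** When both sums are restricted to TPs with a count and a duration, every scenario in the table returns 100%.

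**The case against.** The best defence is that little depends on this variable. Compliance is descriptive, the SAP sets no compliance threshold, and the primary bone mineral density analysis in 6.5.1 does not use it. By-TP eCRF compliance is sound, a second overall ratio is built from the eDiary, and duration, compliance and used tablets are listed, so an affected subject could be found by inspection. All of this stands. It limits the importance of the point but does not make the overall ratio correct.

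A reader might also infer more than the SAP supports:

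- *That compliance is wrong for every subject with incomplete accountability data.* It is not. A TP lacking both count and date leaves the ratio matched. For a subject whose only TP lacks a count, the SAP does not say whether the empty sum is missing or 0, so a false percentage need not appear.
- *That the error is largest in A2 and so distorts the comparison of regimens.* The 50% for A2 assumes two completed 168-day TPs. Under Amendment 9, subjects on six-month courses were to stop at the end of the first or second three months. An A2 subject stopped in her first course has one protocol TP, so the 50% case cannot arise for her, while an A1 or A3 subject stopped after two TPs also shows 50%. No missingness rate is given for any group.
- *That the overall extent of exposure is itself wrong.* It is openly defined as a sum of what is available. It is incomplete when a count is missing, but it is what it claims to be.
- *That the modified SAF is affected.* Its exclusion criteria are set in a separate document, so no effect can be claimed.

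**Conclusion.** The point holds for the overall eCRF compliance ratio. Whenever a TP has a complete tablet count or a duration but not both, numerator and denominator refer to different TPs. A missing count lowers the ratio as if no tablets had been taken; a missing date raises it. The overall eDiary ratio shares only the second fault.

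For one affected TP in a fully adherent subject on the one-year plan, the ratio ranges from 50% to 75% for a missing count and from 133% to 200% for a missing date. These values assume equal TP lengths, one tablet per day and completion of the planned TPs. The real effect depends on how many TPs each subject started before the early stop and on how often counts or dates are missing. The SAP gives neither, so the shift in group summaries cannot be sized, and no ranking of the groups by bias is supported.

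The reach is limited to descriptive compliance tables. The correction is still worth making, because the stated rule yields a wrong number and conflicts with the SAP's own statement that missing eCRF counts are not replaced.

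**What to change.** In 6.1.8.3:

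1. State that overall eCRF compliance is computed only over TPs with both a non-missing tablet count and a non-missing duration, and is missing if a subject has no such TP. Report the number of subjects and TPs omitted.
2. State that for overall eDiary compliance, any TP whose duration is missing is left out of the numerator too.

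In 6.1.8.2, keep overall extent of exposure as the sum of all available tablets and show beside it the number of TPs with missing counts. The matched set of TPs should not be applied to this total: that would discard documented tablets wherever a date is missing, and so understate known exposure in a study whose primary objective is safety.

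The cost is a few sentences, a small change to the derivation of two ratios, and a count line in the exposure and compliance tables. No new data are needed.
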